9. STATISTICAL CONSIDERATIONS

9.1. Statistical Analysis

A Chi Square Test of Independence will be applied to assess whether the prevalence of actionable genotypes is the same in the IPTIP cohort as in existing control datasets (ie. TARDIS and Vanderbilt datasets). ²⁴ The criterion for an actionable variant is as previously detailed (Section 7.0). The primary outcome measure between the IPTIP-I and IPTIP-O cohorts will be compared using the same statistical approach. Statistical differences in genotype based on demography, or recruiting site, will be tested via ANOVA or independent t-test. Logistic regression analysis will be used to determine the predictive value of patient variables, such age, co-morbid status, or ethnicity, for exposure medicines where pharmacogenetic guidelines exist. Statistical support will be provided throughout the trial by an independent trial statistician, [name].

9.2. Sample Size:

Sample Size: Determined based on the primary outcome and calculated with assistance from the NIHR Research Design Service and an independent statistician, [name]. Sample size is calculated using the formula $n=Z^2xPx(1-P)/e^2$ where z is value from standard normal distribution corresponding to desired confidence level (Z=1.96 for 95% CI), P is expected true proportion, e is desired precision.

For the inpatient arm, a previous estimate from Vanderbilt, USA, suggests that 40% of patients had a genetic variant related to a medication that they were prescribed. Given the diversity of the population presenting to MFT and the relative over-medicalisation of healthcare in the USA, a lower prevalence of 0.3 will be chosen to represent P which, with a desired precision of 0.05 and a CI of 95%. This results in a required sample size of **323**.

For the outpatient arm, feasibility trials in Vanderbilt, USA, and the Netherlands suggest that approximately 30% of patients have a genetic variant which would impact prescribing of a medication they were actually prescribed.^{26,27} Therefore, a P of 0.3 will again be used, assuming the same precision and CI as above, generating a required sample size of **323**.

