7. OUTCOME MEASURES

The Primary outcome is the proportion of patients with a genotype related to a medicine they are currently, or have previously been, prescribed. Genotype-phenotype relationships will be assigned where there is high level PharmGKB evidence for clinical actionability (Levels 1A or 1B). Rates for the whole cohort will be presented but will be split by recruiting site and by age. These measures will be used to quantify the potential clinical utility of pre-emptive PGx testing in different settings, directly informing policy decisions around the implementation of PGx nationally.

In addition to the primary outcome, baseline characteristics will be presented. Medicine exposure by British National Formulary (BNF) class will be presented with sub-analysis by age group, sex, and the presence of recorded co-morbidities. Analysis will be presented for the whole cohort, and separately for inpatient and outpatient arms.

Genotype and metaboliser frequencies, derived using CPIC guidelines, will be presented for the whole cohort. These frequencies will then be analysed by age, sex, and ethnicity. Analysis will be presented for the whole cohort, and separately for inpatient and outpatient arms. Statistical differences in genotype based on demography, or recruiting site, will be tested via ANOVA or independent t-test. Genotype frequencies will be compared against an independent control cohort, generated as part of an ongoing trial, genotyping 1500 patients from the TARDIS Trial.²⁵ This will allow for comparison as to whether the dataset generated in this fellowship is consistent with others around the country, so clarifying generalisability.

Finally, the predictive value of patient variables, such age, co-morbid status, or ethnicity, for exposure to medicines where pharmacogenetic guidelines exist will be determined. This will be used to assess whether these variables, either in isolation or in combination, could be used to define a targeted screening approach for pharmacogenetics.

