8. DATA COLLECTION, SOURCE DATA AND CONFIDENTIALITY

8.1. Data Collection at Recruitment

An online recruitment proforma will be completed for each participant by the study team, which will assign the participant with a unique study ID. This online proforma will be part of a bespoke electronic study tool, developed in the MCGM for this study by a web-developer ([name]). This will provide the study team with access to an online recruitment portal. This online tool will be hosted on Manchester University NHS Foundation Trust Servers and will only be accessible within the trust via the intranet (Internally facing). The system builds on existing informatic architecture and will be subject to all legal requirements as outlined by the General Data Protection Regulation (GDPR) and set by the Medicines and Healthcare products Regulatory Agency (MHRA). Initially, the study team will be asked to collect the following details.

- 1. Name
- 2. Date of Birth

- 3. Sex
- 4. NHS Number
- Recruiting site
- 6. Allergy status
- 7. Admission Date (IPTIP-I arm only)
- 8. Participant Reported Current Medicines (IPITIP-O arm only)

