8.3. Prescribing Data Collection and Analysis

Prescribing data for participants from the IPTIP-I arm will also be collected from the discharge summary and from the inpatient prescription chart. This data will be collected by the study team via a dedicated collection tool, also built into the bespoke portal. This can be done at a later timepoint, after recruitment.

Following source data collection, with participant consent, study ID, identifiable demographic, and inpatient prescribing data will be shared with Graphnet CareCentric who operate the Greater Manchester Care Record (GMCR). These records will then be linked with outpatient prescribing data from within the GMCR and deposited as a pseudonymised dataset (labeled with study ID only) available for analysis by the research team within Graphnet's secure data analysis environment. Participant genotype will be then be added to the final dataset within the secure research environment, linked by the Study ID. The final pseudonymised dataset will contain study ID, medicine history, participant genotype and metabolizer status.

The GMCR joins together Greater Manchester's different NHS and care organisations to support hospitals and other care services access individual health and care records quickly and securely. Utilization of the GMCR for the IPTIP trial offers several unique advantages. Firstly, the near 'real-time' data availability enables access to up-to-date prescribing data from the primary care setting in a more reliable and accurate way than is available in other data sources. The data source also provides access to the historical prescribing data of any participant registered with a GP in the conurbation. There is precedent for research and data-sharing such as this using the GMCR and the Graphnet environment. At the time of writing, 15 studies have been approved using GM Care Record Data (https://gmwearebettertogether.com/research-and-planning/). Previously published studies using the GMCR have not sought written consent from participants as the datasets were fully deidentified. Here, as this project first collects the data using the GMCR, extracts it into the Secure

Data Environment known as the Analytics and Data Science Platform (ADSP) to makes use of pseudonymised data for analysis, we will seek consent from participants for data sharing, handling and analysis within a secure environment.

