There will be some infrequent cases where access to the GMCR is not possible for participants, either because the individual has chosen to opt-out of involvement in the GMCR or, more likely, because they are not registered with a GP in Greater Manchester. In these cases, the research team will seek permission from the participants to manually access historical prescribing data via the Summary Care Record (SCR). With a participant's permission, the SCR can be viewed through internal MFT clinical systems or through the Summary Care Record application (SCRa) on the Spine web portal. These data will then be uploaded, alongside the study ID into the final analysis dataset within the secure research environment.

A schematic representation of the data collection, access and analysis process for this project is given in Appendix 1.

The recruitment proforma, containing the "key" to de-anonymize the final dataset, will be stored securely by the senior investigator, [name] for 5 years following the end of the study. After this, the key will be destroyed, rendering the dataset fully anonymous. There is no formal study intervention and participants will not be contacted after the initial enrolment. No participant specific results will be generated and fed back to the participants or their clinician(s).

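### The planned chi-square between IPTIP-I and IPTIP-O cannot separate setting from data source and case-mix, because medicines are captured from different sources in the two arms; a common-source comparison should be added

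*Protocol*

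**What the plan says.** Section 7 defines the outcome: "The Primary outcome is the proportion of patients with a genotype related to a medicine they are currently, or have previously been, prescribed". It also plans its presentation: "Rates for the whole cohort will be presented but will be split by recruiting site and by age".

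Section 9.1 first specifies a test against external control datasets: "A Chi Square Test of Independence will be applied to assess whether the prevalence of actionable genotypes is the same". It then turns to the arms: "The primary outcome measure between the IPTIP-I and IPTIP-O cohorts will be compared using the same statistical approach". No covariate, stratification or restriction by data source is named for this comparison. The logistic regression in the same section models exposure to medicines with pharmacogenetic guidelines, not the primary outcome by arm.

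The medicine sources are set out in Sections 8.1 and 8.3:

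- **Both arms:** "These records will then be linked with outpatient prescribing data from within the GMCR". Where the GMCR cannot be used, the team will, with permission, "manually access historical prescribing data via the Summary Care Record (SCR".
- **IPTIP-I only:** "Prescribing data for participants from the IPTIP-I arm will also be collected from the discharge summary and from the inpatient prescription chart".
- **IPTIP-O only:** the recruitment items include "Participant Reported Current Medicines (IPITIP-O arm only". Section 8.3 does not say whether these entries reach the dataset from which the outcome is derived.

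Section 6.3 asks all participants to consent to access to inpatient prescribing data, but no chart or discharge collection is described for IPTIP-O.

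**The concern.** A participant meets the outcome only if a relevant medicine is found. Adding a source can raise the observed proportion but never lower it. The two arms share one source, and each has a further source that the other lacks, so the chi-square compares two proportions ascertained in different ways.

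The populations differ as well. IPTIP-I takes patients from three hospital wards (Section 6.3.1). IPTIP-O takes genetics clinic attendees and their relatives, carers or partners (Section 6.3.2).

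What is at stake is interpretation. Section 7 says these measures will quantify the potential utility of testing in different settings and inform national policy. Section 4.2 asks which groups would gain most. If the arms differ significantly, the plan gives no means of telling how much is due to setting, how much to the sources searched, and how much to who was recruited.

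**Working it through.** **1. The plan's own figure.** Section 9.2 uses n = Z² × P × (1 − P) / e² with Z = 1.96, P = 0.30 and e = 0.05:

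1.96² × 0.30 × 0.70 / 0.05² = 322.69, rounded up to 323 per arm, 646 in total. This matches the protocol. It is a precision calculation for each arm separately, and the source question does not alter it.

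**2. How the between-arm test reacts to a gap.** The inputs from the protocol are 323 per arm, a 30% rate in both arms, and a two-sided 5% level (taken from Z = 1.96). The size of the gap is an assumption, since the protocol gives no figure for it. For observed rates p1 and p2 with mean p̄ and d = |p1 − p2|:

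- s0 = √(2 p̄ (1 − p̄) / n)
- s1 = √(p1(1 − p1)/n + p2(1 − p2)/n)
- rejection probability = Φ((d − 1.96 s0)/s1) + Φ((−d − 1.96 s0)/s1)

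Worked case, 37% against 30%:

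- p̄ = 0.335
- s0 = √(2 × 0.335 × 0.665 / 323) = 0.0371
- s1 = √((0.37 × 0.63 + 0.30 × 0.70) / 323) = 0.0370
- (0.07 − 1.96 × 0.0371) / 0.0370 is about −0.08, so the probability is about 0.47. The second term is negligible.

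| Assumed capture-only gap | Observed rates | Test rejects |
|---|---|---|
| 0 points | 30% v 30% | 5% |
| 2 points | 32% v 30% | 9% |
| 3 points | 33% v 30% | 13% |
| 5 points | 35% v 30% | 27% |
| 7 points | 37% v 30% | 47% |
| 10 points | 40% v 30% | 76% |

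The smallest observed difference from 30% that reaches significance is about 7.3 points. A 7-point gap needs 10% of otherwise unmatched participants to gain a match from the extra source (0.70 × 0.10 = 0.07).

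**3. The same effect seen as under-capture.** Suppose the true rate is 30% in both arms, IPTIP-I sources find every qualifying participant, and IPTIP-O sources find a share s.

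- s = 0.90: observed rate 27%, test rejects about 14% of the time.
- s = 0.80: observed rate 24%, test rejects about 40% of the time.

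**4. Direction.** The test is two-sided and the formula is symmetric in the arms. If self-reported medicines count and raise IPTIP-O by the same number of points, the rejection probabilities are the same with the sign reversed. The protocol contains nothing from which the net gap could be calculated.

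**The case against.** The strongest reply is that a medicine on an inpatient chart has been prescribed, so it belongs in the outcome as Section 7 defines it. An outpatient has no current inpatient chart to read, and prescribing during admission is part of what makes the inpatient setting different. If 7% of inpatients gain a match from a drug truly prescribed on the ward, 37% is the correct rate, and the 47% above is power to detect a real difference. This stands. A reader might infer that any arm difference would be an artefact of capture, or that the plan is bound to favour inpatient testing. The documents support neither: part of a chart-driven gap is real exposure, the gaps above are assumed, and IPTIP-O has a source of its own.

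It is also fair to say that policy on where to test can properly use crude setting-specific yields. On that view, age and co-morbidity belong to the setting and need not be adjusted away. That is a choice of estimand, and adjustment alone would not cure unequal ascertainment in any case. The protocol already plans rates by recruiting site and by age, and sizes each arm for its own precision.

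A reader might further infer that the pooled rate is invalid because of the two equal targets. That goes too far. Each 323 comes from a precision formula, Section 5.1 gives 646 as a minimum, and the pooled rate is shown beside the split rates. It simply depends on the recruited mix: rates of 40% and 30% pool to 35% at 1:1.

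A separate analysis plan could add a source-restricted analysis. Even so, it is the protocol that fixes both the unequal sources and the unadjusted test, so the limitation belongs in Section 9.1.

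**Conclusion.** The concern holds as a limit on interpretation. The between-arm chi-square mixes three things: real in-hospital prescribing, unequal ascertainment and case-mix. A significant result cannot be attributed to setting, and the net direction of any bias is not fixed by the document. With a 30% true rate in both arms and 323 per arm, capture-only gaps of 5 and 7 points would give rejection rates of about 27% and 47%. Those figures rest on assumed gaps, and they are false-positive rates only for the part of a gap that is not genuine prescribing.

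The primary question in Section 4.1 concerns a proportion. The within-arm proportions and the 323-per-arm precision are unaffected. This is a worthwhile, inexpensive improvement to a between-arm comparison, and not a flaw that undermines the study.

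**What to change.** - Record the source of each prescription (GMCR, SCR, inpatient chart, discharge summary, self-report) before the sources are merged, and state whether self-reported medicines count towards the outcome.
- Keep the all-source rates by arm and describe them as setting-specific yields.
- Add to Section 9.1 a between-arm comparison restricted to the common source (GMCR, or SCR where used), up to recruitment and with the same look-back in both arms.
- Report matches that arise only from chart or discharge medicines as a separate IPTIP-I component.
- Base any statement that the arms differ beyond data source on the common-source comparison.
- Optionally, add a logistic model with arm, age, sex and co-morbidity as a supporting analysis of case-mix.
- The pooled rate may stay if labelled as a description of the recruited sample.

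The cost is one source variable, one extra analysis and a change of wording in Section 9.1. The sample size does not change.

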3. BACKGROUND

3.1. What is the problem being addressed?

It is a well-recognised clinical phenomenon that patients display variation in their response to medicines.¹ Consider three patients in pain, all prescribed the same dose of codeine. The first responds appropriately, the second appears to receive no analgesic relief, whilst the third develops symptoms of opioid toxicity. Such variation in response and side-effects is a frequent and often frustrating feature of clinical practice.

Such variation is regularly attributed to the chosen dosing strategy, the accuracy of the initial diagnosis or individual factors, such as co-morbidities, polypharmacy or compliance.¹ There is evidence that response to a medicine is impacted by an individual's genetic make-up, a concept known as pharmacogenomics. Codeine requires activation to morphine by the hepatic cytochrome CYP2D6.² Common genetic variants in the *CYP2D6* gene impact the function of the CYP2D6 enzyme. Considering the above scenario, the second patient, like 10% of the population, may be a poor CYP2D6 metaboliser, meaning they fail to effectively convert codeine into morphine. Meanwhile, the third patient may represent approximately 2% of individuals who are ultra-rapid CYP2D6 metabolisers, in danger of producing high morphine levels, leading to toxicity.

Codeine is just one example of a medicine with evidence for informing prescribing based on genotype. Good evidence exists for many other commonly prescribed medicines including clopidogrel, tricyclic antidepressants, proton-pump inhibitors (PPIs), statins and anticoagulants.^{3–7} Despite this, clinical implementation, especially in the UK, is limited to a few specific indications, namely azathioprine, abacavir and fluoropyrimidine chemotherapy agents.^{8–10} Current implementation typically involves a "reactive" testing strategy, where patients are tested for genetic variation relating to the medicine they are being prescribed at that moment in time. Many argue

that a prospective testing approach, using gene-panels, is a preferable model. 11-13

Proponents cite the high prevalence of clinically relevant pharmacogenetic variants in the population and the widespread use of medicines for which pharmacogenetic dosing-guidelines exist.

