5. STUDY DESIGN & PROTOCOL

5.1. Participants

A minimum of 646 participants will be recruited across two groups. Participants will be recruited from an outpatient (IPTIP-O) and inpatient (IPTIP-I) setting at the Manchester University NHS Foundation Trust (MFT). As the largest acute hospital trust in the UK, recruitment will access a population from diverse ethnic and socio-economic backgrounds.

- IPTIP-I: Patients admitted to the Manchester Royal Infirmary (MRI) will be recruited. The MRI is large tertiary referral centre with over 750 medical and surgical beds and the Acute Medical Unit (AMU) has a throughput of approximately 200 patients per week.
- IPTIP-O: Patients and their relatives who have an outpatient appointment with the
 Manchester Centre for Genomic Medicine (MCGM) or have previously had an outpatients
 appointment and are still in follow up with the clinical genetics service, will be eligible for
 recruitment. The MCGM serves a population of 5.7 million and there are over 10,000
 appointments each year.

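### Sections 7 and 9.1 test genotype differences with ANOVA or a t-test, although genotype and metaboliser status are multi-class categories with no numeric score

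*Protocol*

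**What the plan says.** The method is fixed twice in the protocol in the same words, in Section 7 (Outcome Measures) and Section 9.1 (Statistical Analysis): "Statistical differences in genotype based on demography, or recruiting site, will be tested via ANOVA or independent t-test".

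Section 7 describes the outcome as a set of frequencies: "Genotype and metaboliser frequencies, derived using CPIC guidelines, will be presented for the whole cohort". It then gives the demographic factors: "These frequencies will then be analysed by age, sex, and ethnicity". Section 8.3 lists what will be held for analysis: "The final pseudonymised dataset will contain study ID, medicine history, participant genotype and metabolizer status". Neither these sections nor any other defines an activity score or other numeric genotype measure.

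For a closely related comparison, Section 9.1 chooses a different method: "A Chi Square Test of Independence will be applied to assess whether the prevalence of actionable genotypes is the same in the IPTIP cohort", set against external control datasets. It uses the same approach to compare the primary outcome between inpatients and outpatients.

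**The concern.** ANOVA and the t-test compare means. A genotype with several classes has no mean until each class is given a number.

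- **Unordered genotypes (diplotypes).** Any numbering is arbitrary, and the p-value changes with it.
- **Metaboliser classes.** These have an order, so scores are less arbitrary. A comparison of mean scores can still hide a real difference: if one group has more poor and also more ultra-rapid metabolisers, the two shifts offset each other.

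The second case matters here because Section 3.1 uses both ends of the CYP2D6 range to motivate the study, with no pain relief at one end and toxicity at the other.

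At stake are the reported comparisons of genotype and metaboliser frequencies by age, sex, ethnicity and recruiting site. The protocol is also inconsistent, since Section 9.1 already uses a categorical test for comparable data.

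**Working it through.** **1. The plan's own figure.** Section 9.2 gives n = Z² × P × (1 − P) / e². With Z = 1.96, P = 0.3 and e = 0.05, this is 3.8416 × 0.21 / 0.0025 = 322.69, rounded up to 323 per arm. Two arms give 646, which agrees with Section 5.1: "A minimum of 646 participants will be recruited across two groups". The point below does not touch this figure. It only supplies the group size for the check.

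**2. Inputs to the check.**
- Group size: 323 against 323, as in the inpatient and outpatient arms. Demographic subgroups will differ in size.
- Class shares from Section 3.1: poor CYP2D6 metabolisers ("like 10% of the population, may be a poor CYP2D6 metaboliser") and about 2% ultra-rapid.
- Assumptions: 30% intermediate and 58% normal, all comparison distributions, the second reference 3/25/67/5, and a two-sided 5% level.

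**3. Method.** Draw multinomial samples for both groups. Score the classes poor, intermediate, normal and ultra-rapid as 0, 1, 2, 3 and apply the pooled t-test (with two groups, ANOVA is the same test). Apply Pearson chi-square to the same counts. Record how often each rejects.

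Mean score = 0 × poor + 1 × intermediate + 2 × normal + 3 × ultra-rapid. For 10/30/58/2 this is 0.30 + 1.16 + 0.06 = 1.52. For 15/20/63/2 it is 0.20 + 1.26 + 0.06 = 1.52, the same mean from a different distribution.

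**4. Results** (shares in per cent, order poor/intermediate/normal/ultra-rapid).

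| Type of difference | Group A | Group B | Means | t-test rejects | Chi-square rejects |
|---|---|---|---|---|---|
| None | 10/30/58/2 | 10/30/58/2 | 1.52, 1.52 | 5% | 5% |
| Exact cancellation, small | 10/30/58/2 | 13/24/61/2 | 1.52, 1.52 | 5% | 33% |
| Exact cancellation, moderate | 10/30/58/2 | 15/20/63/2 | 1.52, 1.52 | 5% | 78% |
| Exact cancellation, large | 10/30/58/2 | 17/16/65/2 | 1.52, 1.52 | 5% | 98% |
| Exact cancellation, both tails up | 10/30/58/2 | 15/25/53/7 | 1.52, 1.52 | 5% | 92% |
| Exact cancellation, both tails up | 3/25/67/5 | 7/25/55/13 | 1.74, 1.74 | 5% | 98% |
| Partial cancellation | 3/25/67/5 | 7/25/60/8 | 1.74, 1.69 | 16% | 70% |
| Ordered shift | 10/30/58/2 | 13/35/50/2 | 1.52, 1.41 | 49% | 39% |
| Ordered shift | 3/25/67/5 | 6/30/60/4 | 1.74, 1.62 | 68% | 54% |

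**5. Dependence on the coding.** Treat the four classes as unordered labels, as diplotypes are, and compare 10/30/58/2 with 15/20/63/2 under three numberings:
- 0/1/2/3: means 1.52 and 1.52, t-test power 5%.
- 1/0/2/3: means 1.32 and 1.47, power 58%.
- 2/0/1/3: means 0.84 and 0.99, power about 81%.

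Chi-square does not use the labels and stays at about 78% throughout.

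**6. Two-class case.** For a yes/no variant at 0.30 against 0.40, both tests have 76% power. With no difference, both reject about 5% of the time, at a prevalence of 0.3 and of 0.02.

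**The case against.** The strongest reply is that little depends on this sentence. The primary outcome is a proportion, and its comparison between arms already uses chi-square. The sample size rests on that proportion. The secondary question about groups of heightened value is served by logistic regression. The genotype comparisons are supporting description, and Section 8.3 says that no individual results are fed back. The test can be changed at analysis without new data. All of this stands, and it limits the importance of the point.

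It is also fair to say that equal means are a worst case. The t-test's 5% there follows from the construction, the class frequencies are largely assumed, and for ordered shifts the scored t-test is the more powerful of the two. The opposite-tails argument applies only to genes that have an increased-function class. These limits stand as well, which is why the table covers the whole range.

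One might read the sentence as comparing mean age across genotype groups, for which ANOVA is legitimate. That reading does not cover sex, ethnicity or recruiting site, so it does not rescue the text.

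Two stronger conclusions are tempting but unsupported:
- **That the tests are invalid and produce false positives.** In the check, type I error stayed near 5% with four scored classes and with two.
- **That the choice creates a multiplicity problem**, since Section 8.2 describes a panel of 20 genes and several factors are examined. Any test at the same level would share that problem. The protocol does not say that every gene is tested against every factor, and multiplicity handling is commonly left to the analysis plan, which is not shown.

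**Conclusion.** The text is wrong as written and should be corrected. It names a test of means, in two places, for categorical outcomes with no defined score, while the same section uses a suitable test for similar data. An analysis plan that follows the protocol would inherit the choice.

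The faults are mismatch, dependence on an unstated coding, and loss of power against differences that wholly or partly cancel in the mean. In the cases tried, the scored t-test ranged from no power beyond its 5% error rate (exact cancellation) to a modest advantage over chi-square (ordered shifts). On coding alone, its power moved from 5% to about 81%. These sizes rest on the assumed class frequencies and on 323 per group. That the test is undefined for unordered genotypes rests on no assumption.

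No consequence follows for the primary result or for the planned sample size.

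**What to change.** In Sections 7 and 9.1, replace ANOVA and the t-test by a chi-square test of independence for genotype and metaboliser frequencies, with an exact or Monte Carlo version where cells are sparse. Where metaboliser classes are treated as ordered, or age is kept continuous, add a trend test or an ordinal or multinomial logistic regression.

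The cost is two sentences of protocol text, with no new data and no burden on participants. The one statistical drawback is that chi-square alone has somewhat less power against ordered shifts (39% against 49%, and 54% against 68%, in the cases above). The trend or ordinal method covers this. Finer rules, such as when a cell counts as sparse, can be left to the analysis plan.

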There is evidence to support genotype-guided prescribing for a range of medicines and the cost of genetic sequencing has fallen to allow use in clinical practice. Despite this, there are remaining barriers to prospective pharmacogenetic testing, as evidenced by the lack of clinical implementation across the UK. These barriers were recently discussed as part of a policy discussion, and the contributors specifically highlighted a paucity of evidence around real-world clinical utility. The IPTIP trial aims to address this, by determining the clinical utility of pharmacogenetic data using both historical and contemporaneous prescribing data.

In this proposal, clinical utility refers to the concept that an individual would have their prescription altered based on their genotype. A cross-sectional survey of US veterans found 99% carried an actionable pharmacogenetic variant. However, many of these variants were related to the metabolism of medications that the patient is not prescribed; therefore, clinical utility in those patients is low. Defining the clinical utility of pharmacogenetics on a more granular level is critical when considering implementation strategies. If overall clinical utility is high, then a pre-emptive panel approach is likely to be a practical approach, otherwise, more targeted testing strategies may be appropriate. The integration of pharmacogenetics within clinical practice represents a complex intervention, as defined by the Medical Research Council, and causal assumptions which underpin any intervention should be well characterised before implementation. By linking genotype and detailed prescribing data, the IPTIP trial will define clinical utility and identify cohorts where pharmacogenetic testing is of particular benefit.

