4. STUDY OBJECTIVES

4.1. Primary Question/Objective:

If a pre-emptive pharmacogenetic test were implemented, what proportion of patients would have their prescriptions adjusted based on the results?

4.2. Secondary Question/Objective:

Are there specific groups of patients in whom pre-emptive screening would be of heightened value?

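### The only model offered for targeting screening predicts exposure to a guideline medicine, not the gene-drug match that the protocol treats as utility

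*Protocol*

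**What the plan says.** Objective 4.2 of the protocol asks: "Are there specific groups of patients in whom pre-emptive screening would be of heightened value"? Section 3.1 states what value means here: "clinical utility refers to the concept that an individual would have their prescription altered based on their genotype". It adds that utility is low where a variant concerns a medicine the patient does not take, and it names the linkage of genotype with prescribing data as the means of finding the cohorts that benefit.

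The primary outcome in Section 7 follows that definition: "the proportion of patients with a genotype related to a medicine they are currently, or have previously been, prescribed".

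The model meant for targeting does not. Section 7 says the predictive value of patient variables "for exposure to medicines where pharmacogenetic guidelines exist will be determined", and that this will be used to judge whether the variables, singly or together, "could be used to define a targeted screening approach for pharmacogenetics". Section 9.1 repeats the outcome: logistic regression for "the predictive value of patient variables, such age, co-morbid status, or ethnicity, for exposure medicines where pharmacogenetic guidelines exist".

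Two other analyses touch on subgroups. For the primary outcome, "Rates for the whole cohort will be presented but will be split by recruiting site and by age", and Section 9.1 adds a chi-square comparison between the inpatient and outpatient arms. For genotype and metaboliser status, "These frequencies will then be analysed by age, sex, and ethnicity", and differences by recruiting site are also tested.

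**The concern.** By the protocol's own definition, a person gains from the test when two things coincide: a relevant medicine and an actionable genotype for it. The regression models only the first. Genotype enters neither its outcome nor its named predictors, so it could be fitted without genotyping anyone.

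The ranking of groups is at stake. If relevant-genotype frequency differs between groups, one with ordinary prescribing and many relevant genotypes may look unremarkable. A group with heavy prescribing and few relevant genotypes may look like a priority. Section 7 says the utility measures are meant to inform national policy, so the model used to propose whom to test should describe the same quantity.

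**Working it through.** **The plan's own figure.** Section 9.2 gives P = 0.3, e = 0.05 and Z = 1.96. Then n = Z² × P × (1 − P) / e² = 3.8416 × 0.21 / 0.0025 = 322.69, rounded up to 323 per arm and 646 in total. This reproduces, and nothing below alters it.

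**What is planned, by outcome and factor.**

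| Outcome | Factors examined |
|---|---|
| Gene-drug match (primary outcome) | site, age |
| Genotype or metaboliser status | age, sex, ethnicity, site |
| Exposure to guideline medicines (logistic model) | variables such as age, co-morbidity, ethnicity, alone or combined |

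The match does not meet ethnicity, sex or co-morbidity in any row, and the only multivariable model is in the third row.

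**Relation between the two outcomes.** Let E be the probability of exposure in a group, and G the probability that an exposed person carries an actionable genotype for a medicine taken. Then P(match) = E × G. If G is the same in all groups, the match rate rises and falls with E and both outcomes rank groups alike. If G varies, they need not.

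**Illustrations.** The documents give no exposure rates and no relevant-genotype rates by group, so every E and G below is an assumption. OR = [p1/(1 − p1)] / [p2/(1 − p2)], group 1 against group 2.

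| E, group 1 v 2 | G, group 1 v 2 | Match, group 1 v 2 | Exposure OR | Match OR |
|---|---|---|---|---|
| 70% v 50% | 40% v 40% | 28% v 20% | 2.33 | 1.56 |
| 60% v 60% | 55% v 45% | 33% v 27% | 1.00 | 1.33 |
| 60% v 60% | 60% v 40% | 36% v 24% | 1.00 | 1.78 |
| 70% v 70% | 40% v 20% | 28% v 14% | 1.00 | 2.39 |
| 60% v 60% | 70% v 35% | 42% v 21% | 1.00 | 2.72 |
| 70% v 50% | 35% v 60% | 24.5% v 30% | 2.33 | 0.76 |

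For the fourth row: 0.7 × 0.4 = 0.28 and 0.7 × 0.2 = 0.14, so OR = (0.28/0.72) / (0.14/0.86) = 0.389/0.163 = 2.39. In the first row the genotype rates are equal and the two outcomes rank the groups alike. In the next four the exposure model sees no difference where the match differs. In the last row the ranking reverses.

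**Could the study support a match model?** With P = 0.3 in both arms, 646 × 0.3 = 193.8, or about 194 events. At the customary 10 events per parameter that carries about 19 parameters. For 36% against 24%, which averages the planned 30% in equal groups, a two-sided 5% comparison has about 92% power with groups of 323 and 323, and about 78% with 517 and 129.

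**The case against.** Exposure is a sensible thing to model. Without a relevant medicine there is no match, and Section 3.1 cites a US veterans survey in which 99% carried some actionable variant. On that view prescribing, not genotype, decides who benefits. No figure in the documents shows genotype varying with age or co-morbidity, two of the three predictors that Section 9.1 names, so the concern bites mainly for ethnicity. The question is secondary, and nothing in Section 9.1 forbids a further model.

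Much of this stands. The exposure model is informative, and it ranks groups correctly where genotype frequency is constant across the predictor. The 99%, however, counts any variant, not one relevant to a medicine taken. The plan's own expected match proportion is 0.3. If exposure were 60% (an assumption), half of those exposed would have no match (0.3/0.6 = 0.5). The protocol also plans to test whether genotype differs by demography, so it cannot take constancy for granted.

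Nor is this a detail left to a statistical analysis plan, since the protocol states the dependent variable in two sections. The reporting of discrimination and calibration can be left there.

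A reader might infer that objective 4.2 goes unanswered, or that the plan overlooks ethnic differences in genotype. Neither follows: the match is split by site and age and compared between arms, and genotype is analysed by ethnicity. A reader might also expect exposure to be near-universal in older inpatients, leaving nothing to predict. The documents give no exposure rate, so that cannot be claimed.

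**Conclusion.** The point holds in a limited form. The one model put forward for defining targeted screening has an outcome that differs from the protocol's definition of utility and from its primary outcome, and no other planned analysis relates the match to ethnicity, sex or co-morbidity, alone or in combination. By itself, the exposure model can be relied on to rank groups by utility only if relevant-genotype frequency does not vary with the predictors.

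The size of any mis-ranking here is unknown. Under the assumed rates with equal exposure and differing genotype rates, match odds ratios run from 1.33 to 2.72 while the exposure odds ratio stays at 1.0. One assumed pattern reverses the order of the groups. These cases show that the two outcomes can diverge, not that they will in this cohort. The primary estimate and the 323 per arm are unaffected.

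**What to change.** In Sections 7 and 9.1, name the primary-outcome match (yes/no) as the dependent variable of the main logistic model for objective 4.2, with the predictors already listed, and keep the exposure model as supportive. Reading the two together would also show whether a group stands out because of its prescribing or its genotypes.

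The cost is a sentence in each section and one more model. Section 8.3 already links medicine history and genotype for each participant, and the predictors are those the planned regression needs anyway. The sample size stays at 646.
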